Template No: CS_TP_BS016 – Revision 3

Reference: CS_WI_BS005

Effective Date: 01May2012

Copyright © 2012 [REDACTED] All rights reserved.

The contents of this document are confidential and proprietary to [REDACTED]. Unauthorized use, disclosure or reproduction is strictly prohibited.

variables will be the observed values of the efficacy variables over time, including the baseline value. Patients will be classified into two separate patterns: dropouts and completers. To illustrate, only two treatment groups are considered. Let y_{ij} represent the response value of the i th subject at time j (i.e., actual day of assessment), the following random effects pattern mixture model with an unstructured covariance matrix is fitted:

$$y_{ij} = \beta_0 + \beta_1 Time_{ij} + \beta_2 Treat_i + \beta_3 (Treat_i \times Time_{ij}) + \beta_4 Drop_i + \beta_5 (Drop_i \times Time_{ij}) + \beta_6 (Drop_i \times Treat_i) + \beta_7 (Drop_i \times Treat_i \times Time_{ij}) + v_{0i} + v_{1i} Time_{ij} + \epsilon_{ij} \quad (1)$$

Where:

Drop = 0 for completers, and 1 for dropouts

Treat = 0 for patients in the placebo group, and 1 for patients in the SM-13496 treatment group

The random intercept v_{0i} and random time effect v_{1i} are assumed to follow a bivariate normal distribution, and the model residuals ϵ_{ij} are assumed to be independently distributed and follow a univariate normal distribution.

Based on the above specified random effects pattern mixture model, the parameter estimates for fixed effects (intercept, time, treatment, treatment-by-time, dropout pattern, dropout pattern-by-time, dropout pattern-by-treatment, and dropout pattern-by-treatment-by-time) as well as the covariance matrix for the parameter estimates will be obtained by using the SAS PROC MIXED procedure.

Substituting Drop = 0 and 1 in the above random effects pattern mixture model (1), the following regression models for completers and dropouts can be obtained. The model for completers is:

$$y_{ij} = \beta_0 + \beta_1 Time_{ij} + \beta_2 Treat_i + \beta_3 (Treat_i \times Time_{ij}) + v_{0i} + v_{1i} Time_{ij} + \epsilon_{ij} \quad (2)$$

and the model for dropouts is:

$$y_{ij} = (\beta_0 + \beta_4) + (\beta_1 + \beta_5) Time_{ij} + (\beta_2 + \beta_6) Treat_i + (\beta_3 + \beta_7) (Treat_i \times Time_{ij}) + v_{0i} + v_{1i} Time_{ij} + \epsilon_{ij} \quad (3)$$

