15.1.4.3. Pattern Mixture Model with Placebo-based Multiple Imputation

A pattern-mixture model using a placebo-based multiple imputation method will be performed as a second sensitivity analysis to explore the robustness of the MMRM results for the primary and key secondary efficacy variables for the ITT population. This method was based on methodology proposed by Ratitch and O'Kelly (Ratitch & O'Kelly, 2011). The assumption that efficacy profiles of dropouts after discontinuation are similar to those of placebo patients is considered conservative because this methodology tends to minimize the difference between SM-13496 and placebo groups. If the results of this analysis are in line with the primary efficacy results, then it can be confidently concluded that the primary analysis results are robust.

Using this method, missing data after dropout will be imputed based on placebo group data using multiple imputation methodology for all patients (including active treatment patients).

The steps to implement this sensitivity analysis are as follows:

1. 1000 datasets will be generated where missing data at intermediate visit(s) will be imputed for each treatment group using non-missing data from all patients within the treatment group by a Monte Carlo Markov Chain (MCMC) imputation model using the MCMC statement in the SAS PROC MI procedure. As a result, each dataset will only have missing ending data, or a monotone missing data pattern.
2. For each dataset from Step 1, missing ending data will be imputed based on information from the placebo group. As a result, 1000 imputed complete datasets will be generated.
 - Missing data at the first post-baseline visit will be imputed by a regression imputation model using the SAS PROC MI procedure with the REGRESSION option in the MONOTONE statement.
 - The SAS PROC MI procedure will use data from all placebo patients as well as SM-13496 patients with missing data at the visit (i.e., only those that need imputation at the visit). Because patients

Document: K:\DSP\SM-13496\KVA95374\Biostatistics\Documentation\SAP
 Author: [REDACTED] Version Number: 1.0
 Version Date: 30MAR2017

Template No: CS_TP_BS016 – Revision 3 Reference: CS_WI_BS005
 Effective Date: 01May2012

Copyright © 2012 [REDACTED] All rights reserved. [REDACTED] Unauthorized use, disclosure or reproduction is strictly prohibited.

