APPENDIX 3. SAS CODE

Treatment: TRTPN
Analysis visit: AVISIT

1. Mixed Model Repeated Measures (MMRM) Analysis

Note: Ensure that input dataset is sorted by USUBJID AVISIT prior to initiating the MIXED procedure.

```
ods output estimates=outset /*Output from estimate statement*/  
diffs=outdiff /*Treatment Group Comparison*/  
R=outr /*R matrix */  
lsmeans=outlsmean; /*LSmeans of each treatment group*/
```

```
PROC MIXED;  
CLASS SUBJID POOLSITE TRTPN AVISIT;  
MODEL CFB = BASE POOLSITE TRTPN AVISIT TRTPN*AVISIT/DDFM=KR;  
REPEATED AVISIT /TYPE=UN SUBJECT=SUBJID R;  
LSMEANS TRTPN* AVISIT /PDIFF CL;  
ESTIMATE 'LINEAR TREND TEST FOR DOSE RESPONSE'  
TRTPN 0 1 -1 TRTPN*AVISIT 0 0 0 0 0 0 0 0 0 0 0 0 0 1  
0 0 0 0 0 0 -1/CL;  
ESTIMATE 'DOSE-RESPONSE 20-60 vs 80-120' TRTPN -1 1 0 TRTPN*AVISIT  
0 0 0 0 0 0 -1 0 0 0 0 0 0 1 0 0 0 0 0 0 0/CL;  
RUN;
```

a. Mixed Model Repeated Measures (MMRM) Analysis for the case above
model fails to converge

```
PROC MIXED empirical;
```

Document:	K:\DSP\SM-13496\KVA95374\Biostatistics\Documentation\SAP	Version Number:	1.0
Author:	[REDACTED]	Version Date:	30MAR2017

Template No: CS_TP_BS016 – Revision 3
Effective Date: 01May2012

Reference: CS_WI_BS005

Copyright © 2012 [REDACTED] All rights reserved.
The contents of this document are confidential and proprietary to [REDACTED]. Unauthorized use, disclosure or reproduction is strictly prohibited.

```
CLASS SUBJID POOLSITE TRTPN AVISIT;  
MODEL TOTCFB = TOTBL POOLSITE TRTPN AVISIT TRTPN*AVISIT;  
REPEATED AVISIT /TYPE=XXX SUBJECT=SUBJID R;  
LSMEANS TRTPN*AVISIT /PDIFF CL;  
ESTIMATE 'LINEAR TREND TEST FOR DOSE RESPONSE'  
TRTPN 0 1 -1 TRTPN*AVISIT 0 0 0 0 0 0 0 0 0 0 0 0 1  
0 0 0 0 0 0 -1/CL;  
ESTIMATE 'DOSE-RESPONSE 20 vs 80-160' TRTPN -1 1 0 TRTPN*  
AVISIT 0 0 0 0 0 0 -1 0 0 0 0 0 0 1 0 0 0 0 0 0/CL;  
RUN;
```

XXX: application order
Heterogeneous Toeplitz (TYPE=TOEPH)
Heterogeneous first-order autoregressive (TYPE=ARH(1))
Toeplitz (TYPE=TOEP)

2. Analysis of Covariance

```
PROC MIXED;  
CLASS TRTPN POOLSITE;  
MODEL CFB = TRTPN POOLSITE BASE;  
LSMEANS TRTPN / PDIFF CL;  
ESTIMATE 'LINEAR TREND' TRTPN 0 1 -1 /CL;  
ESTIMATE 'DOSE-RESPONSE 20 vs 80-160' TRTPN -1 1 0/CL;  
RUN;
```

3. Sensitivity Analysis

a. Random Effects Pattern Model

```
If TRT01PN=1 then DOSE1=1 else DOSE1=0;  
If TRT01PN=2 then DOSE2=1 else DOSE2=0;  
If COMPLFL="Y" then DROP=1 else DROP=0;
```

```
PROC MIXED;  
CLASS USUBJID;  
MODEL AVAL = QSDAY DOSE1 DOSE2 QSDAY*DOSE1 QSDAY*DOSE2  

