SOLUTION COVB DDFM = KR;
RANDOM INTERCEPT DAY /SUB=USUBJID TYPE=UN G;
RUN;

b. Multiple Imputation

NOTE: Placebo based imputation

```
PROC MI
VAR SITEGR1N SCORE_1 SCORE_2 SCORE_3 SCORE_4 SCORE_5 SCORE_6
SCORE_7;
BY TRT01PN;
MCMC CHAIN=MULTIPLE IMPUTE=MONOTONE;
RUN;

%MACRO MI_IMP(INDATA=, ANVIS=, SEED=, VAR1=, VAR2=, OUTDATA=);
DATA EFF_MONO_IMP EFF_MONO_REST;
SET &INDATA;
IF TRT01PN IN (2,3) AND LASTVIS >=&ANVIS THEN OUTPUT
EFF_MONO_REST;
ELSE OUTPUT EFF_MONO_IMP;
RUN;

PROC SORT DATA= EFF_MONO_IMP;
BY _IMPUTATION_;
RUN;

PROC MI DATA=EFF_MONO_IMP OUT=EFF_REG_IMP NIMPUTE=1 SEED=&SEED
MINIMUM=0 MAXIMUM=60;
VAR &VAR1 &VAR2;
BY _IMPUTATION_;
MONOTONE REGRESSION(&VAR2= &VAR1 / DETAILS);
RUN;

DATA &OUTDATA;
SET EFF_MONO_REST EFF_REG_IMP;
RUN;

PROC DATASETS;
DELETE EFF_MONO_IMP EFF_MONO_REST EFF_REG_IMP;
RUN;
%MEND MI_IMP;
```

Document: K:\DSP\SM-13496\KVA95374\Biostatistics\Documentation\SAP
Author: [REDACTED] Version Number: 1.0
Version Date: 30MAR2017

Template No: CS_TP_BS016 – Revision 3
Effective Date: 01May2012

Reference: CS_WI_BS005

Copyright © 2012 [REDACTED] All rights reserved.
The contents of this document are confidential and proprietary to [REDACTED]. Unauthorized use, disclosure or reproduction is strictly prohibited.

```
%MI_IMP(INDATA=EFF_MONO, ANVIS=2, SEED=445566, VAR1=SCORE_1 SCORE_2,  
VAR2=SCORE_3, OUTDATA=EFF_IMP1);  
%MI_IMP(INDATA=EFF_IMP1, ANVIS=3, SEED=445566, VAR1=SCORE_1 SCORE_2  
SCORE_3, VAR2=SCORE_4, OUTDATA=EFF_IMP2);  
%MI_IMP(INDATA=EFF_IMP2, ANVIS=4, SEED=445566, VAR1=SCORE_1 SCORE_2  
SCORE_3 SCORE_4, VAR2=SCORE_5, OUTDATA=EFF_IMP3);  
%MI_IMP(INDATA=EFF_IMP3, ANVIS=5, SEED=445566, VAR1=SCORE_1 SCORE_2  
SCORE_3 SCORE_4 SCORE_5, VAR2=SCORE_6, OUTDATA=EFF_IMP4);  
%MI_IMP(INDATA=EFF_IMP4, ANVIS=6, SEED=445566, VAR1=SCORE_1 SCORE_2  
SCORE_3 SCORE_4 SCORE_5 SCORE_6, VAR2=SCORE_7, OUTDATA=EFF_IMP5);
```

```
DATA MI_EFF;  
  SET EFF_IMP5;  
  AVISITN=1;  
  DIFF=SCORE_2-SCORE_1;  
  OUTPUT;  
  AVISITN=2;  
  DIFF=SCORE_3-SCORE_1;  
  OUTPUT;  
  AVISITN=3;  
  DIFF=SCORE_4-SCORE_1;  
  OUTPUT;  
  AVISITN=4;  
  DIFF=SCORE_5-SCORE_1;  
  OUTPUT;  
  AVISITN=5;  
  DIFF=SCORE_6-SCORE_1;  
  OUTPUT;  
  AVISITN=6;  
  DIFF=SCORE_7-SCORE_1;  
  OUTPUT;
```

```
RUN;
```

```
ods listing close;
```

```
PROC MIXED;
```

```
  CLASS USUBJID TRT01PN AVISITN SITEGR1N;  
  MODEL      DIFF=SCORE_1      TRT01PN      AVISITN      SITEGR1N  
TR01PN*AVISITN/DDFM=KR SOLUTION CL;  
  REPEATED AVISITN /SUBJECT=USUBJID TYPE=UN;
```

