Document:	K:\DSP\SM-13496\KVA95374\Biostatistics\Documentation\SAP	Version Number:	1.0
Author:	[REDACTED]	Version Date:	30MAR2017

Template No: CS_TP_BS016 – Revision 3
Effective Date: 01May2012

Reference: CS_WI_BS005

Copyright © 2012 [REDACTED] All rights reserved.
The contents of this document are confidential and proprietary to [REDACTED]
reproduction is strictly prohibited.

Unauthorized use, disclosure or

```
LSMEANS TRT01PN*AVISITN / DIFF=CONTROL("1", "6")diff=control("1"
"6") CL;
BY _imputation_;
RUN;
```

```
PROC MIANALYZE;
CLASS TRT01PN;
BY _TRT01PN;
MODELEFFECTS TRT01PN;
run;
```

```
proc mianalyze parms=ls_mean;
CLASS TRT01PN;
BY AVISITN;
MODELEFFECTS TRT01PN;
RUN;
```

4. MADRS 50% Responders Logistic Model

Note: Placebo will be reference

Note: All SM-13496 groups will be included in a model

```
PROC LOGISTIC DESCENDING;
CLASS TRTPN POOLSITE / PARAM=REF;
MODEL RESP50 = TRTPN POOLSITE BASE;
CONTRAST 'LUR 20-60 vs. PLACEBO' TRTPN 1 0/ESTIMATE=EXP;
CONTRAST 'LUR 80-120 vs. PLACEBO' TRTPN 0 1/ESTIMATE=EXP;
RUN;
```

5. Ranked ANCOVA (Selected Safety Parameters)

```
PROC RANK OUT= OUT1 NPLUS1 TIES = MEAN;
VAR VSCFB VSBASE;
RANKS RKVSCFB RKVSBASE;
RUN;
```

```
PROC GLM DATA = OUT1;
MODEL RKVSCFB = RKVSBASE;
OUTPUT OUT=RESIDUAL R=RESID;
RUN;
```

```
PROC FREQ DATA = RESIDUAL;
TABLES TRTPN*RESID / NOPRINT CMH2;
RUN;
```

6. NNT and 95% CI

Document: K:\DSP\SM-13496\KVA95374\Biostatistics\Documentation\SAP

Author: [REDACTED]

Version Number:

1.0

Version Date:

30MAR2017

Template No: CS_TP_BS016 – Revision 3

Reference: CS_WI_BS005

Effective Date: 01May2012

Copyright © 2012 [REDACTED] All rights reserved.

The contents of this document are confidential and proprietary to [REDACTED] reproduction is strictly prohibited.

[REDACTED] Unauthorized use, disclosure or

```
pi0a: responder rate of SM-13496 group
pi1: responder rate of placebo group
delta_ua : upper limit of NNT before taking the reciprocal
delta_la : lower limit of NNT before taking the reciprocal

nnt = round(1/(pi0a - pi1), 0.01);
delta_la = pi0a - pi1 - 1.96*sqrt(pi1*(1-pi1)/PCOUNT + pi0a*(1-
pi0a)/COUNT);
delta_ua = pi0a - pi1 + 1.96*sqrt(pi1*(1-pi1)/PCOUNT + pi0a*(1-
pi0a)/COUNT);

if pi0a>=pi1 then do;
    lower_ba = min(delta_ua, 1);
    upper_ba = max(delta_la, 0.000001);
end;
else if pi0a<pi1 then do;
    lower_ba = min(delta_ua, -0.000001);
    upper_ba = max(delta_la, -1);
end;

lcia = floor(round(1/lower_ba));
ucia = ceil(round(1/upper_ba));

* CA test */

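### SAP Appendix 3 codes the treatment arms in two incompatible ways, so its two missing-data sensitivity analyses cannot both use placebo alone as reference or donor arm

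*SAP*

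**What the plan says.** **The text.** SAP 15.1.4.2 defines the random effects pattern mixture model with "Treat = 0 for patients in the placebo group, and 1 for patients in the SM-13496 treatment group", and with "Drop = 0 for completers, and 1 for dropouts". SAP 15.1.4.3 specifies that "missing ending data will be imputed based on information from the placebo group", and keeps lurasidone patients observed at a visit out of the imputation model for that visit.

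**The code, item 3a.** The dose indicators are "If TRT01PN=1 then DOSE1=1 else DOSE1=0" and "If TRT01PN=2 then DOSE2=1 else DOSE2=0". The comments in the IML step label these terms as differences from control. The dropout flag is "If COMPLFL='Y' then DROP=1 else DROP=0".

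**The code, item 3b.** The line "IF TRT01PN IN (2,3) AND LASTVIS >=&ANVIS THEN OUTPUT" sets aside the observed patients of two arms, so that only the remaining arm supplies observed data to the imputation model. The comparison line begins "LSMEANS TRT01PN*AVISITN / DIFF=CONTROL('1', '6", which makes code 1 the control.

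**The code list.** The SAP gives no list of values for TRT01PN or TRTPN, and the indirect signs disagree:
- Appendix 1 puts placebo first in tables and last in listings.
- The TRTPN coefficients in the MMRM and logistic code fit placebo as the last level.
- The note to the trend test gives placebo the value 0.
- The weight indices in 3a run 1, 2, 3 for control, first dose and second dose, which hints at placebo coded 1.

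**The concern.** Items 3a and 3b are the two analyses the SAP adds to examine departures from the missing-at-random assumption behind the primary MMRM. Agreement between the 3a model and its counterpart without dropout pattern is to be read as support for that assumption. Agreement between 3b and the MMRM is to be read as robustness, on the ground that imputing from placebo is conservative. If the arm lists are carried into the programs as printed, at least one of these analyses does not do what the text describes. A wrong arm list or a reversed flag is a matter of meaning, so correcting the syntax would not reveal it.

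**Working it through.** **1. Is there a coding that works?** Item 3a has placebo alone as reference only if the active codes are {1,2}. Item 3b has placebo alone as donor only if the active codes are {2,3}. These cannot both be true. Listing all 24 assignments of three arms to codes 0-3 gives:
- placebo alone as the 3a reference: 4
- placebo alone as the 3b donor: 4, of which 2 also have placebo at control level 1
- both blocks right: 0

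Allowing codes 0-4 (60 assignments) also gives 0. Examples:

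| Placebo, 20-60, 80-120 | 3a reference | 3b donor |
|---|---|---|
| 1, 2, 3 | 80-120 mg | placebo |
| 3, 1, 2 | placebo | 20-60 mg |
| 0, 1, 2 | placebo | placebo + 20-60 mg |
| 0, 2, 3 | placebo + 80-120 mg | placebo |

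**2. Inputs for size.** Protocol 3.5 gives a 3.5-point effect in both doses, SD 10 and 161 per arm. SE of a difference = 10 × √(2/161) = 1.11. SAP 15.1.4.2 gives 17.4% overall dropout. Dropout by arm is not given, so placebo dropout p is varied from 12% to 25% (an assumption), with active dropout a = (3 × 0.174 − p)/2.

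**3. Item 3b, placebo coded 3 and 20-60 mg coded 1, only the control level corrected.** Let each dropout take the donor-arm mean.
- Intended (placebo donor): active dropouts lose the effect, so the difference is 3.5 × (1 − a).
- As coded (20-60 mg donor): active dropouts keep the effect and placebo dropouts gain it, so the difference is 3.5 × (1 − p).

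| p | a | Intended | As coded | Shift |
|---|---|---|---|---|
| 12% | 20.1% | 2.80 | 3.08 | +0.28 (0.25 SE) |
| 17.4% | 17.4% | 2.89 | 2.89 | 0 |
| 25% | 13.6% | 3.02 | 2.62 | −0.40 (0.36 SE) |

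The SAP regresses on previous visits instead. A simulation of that method (150,000 per arm, visit correlations 0.5, 0.7 and 0.85, linear build-up of effect) gave shifts of +0.19 to +0.23, about 0, and −0.31 to −0.35.

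**4. Item 3b with the control level left at 1.** The simulated output is placebo minus 20-60 mg (+2.7 to +3.3, reversed sign) and 80-120 mg minus 20-60 mg (about 0).

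**5. Item 3a with placebo coded 1 and 20-60 mg coded 2.** On one simulated trial the log-likelihood is −8598.33 whether placebo or 80-120 mg is the reference. The 20-60 mg versus placebo slope difference over 42 days in completers is −3.06 both directly and as DOSE2 − DOSE1. The model is only reparameterised, but the printed terms, labels and pattern weights are not the intended dose-versus-placebo ones.

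**6. The reversed flag in 3a.** The IML rows treat DROP = 0 as completers. If the undefined `&grp1x` variables count completers, as their comments say, the weights 0.826 and 0.174 are exchanged. With effect c in completers and d in dropouts, the intended value is 0.826c + 0.174d and the value obtained is 0.174c + 0.826d. For c = 3.5:
- d = 0: 2.89 becomes 0.61
- d = 1.75: 3.20 becomes 2.05
- d = 3.5: 3.50 in both

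If `&grp1x` counts patients with DROP = 0, only the completer and dropout labels are exchanged.

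**The case against.** The strongest reply is that this is template code overridden by clear text. Sections 15.1.4.2 and 15.1.4.3 name placebo unambiguously, and the code cannot run as printed. The IF/ELSE lines lack a semicolon, the LSMEANS line repeats an option, and some variable names are misspelled. A programmer must therefore rewrite several of the disputed lines anyway. The weight indices in 3a suggest placebo coded 1, under which 3b is right and 3a is only reparameterised. The donor-arm error needs a particular coding and a partial correction, and is small even then. Reversed contrasts would probably be noticed. The flag is a separate slip, its largest figure assumes no effect in dropouts, and 3a reports intercepts and slopes, not a Week 6 difference. A value list may exist in dataset specifications that were not supplied. The LOCF ANCOVA, the dropout plot and the per-protocol analysis remain.

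Much of this stands as a limit on size. It does not remove the fault. Repairing the syntax leaves the codes unchanged, and the IN (2,3) line needs no syntax repair at all. The hint from the weight indices conflicts with the TRTPN contrasts. Under placebo coded 1, the reference, labels and weights in 3a are still wrong. Both treatment terms in 3a carry the same pattern weights, so exchanged weights pass through to any Week 6 contrast built from them.

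**Conclusion.** The concern holds: as printed, no coding of TRT01PN makes both blocks agree with the SAP text, and the dropout flag in 3a is reversed. The fault lies in sample code. It does not reach the primary MMRM comparisons or the Hochberg decision, and neither sensitivity analysis carries alpha. The donor-arm error in 3b is worth nothing at equal dropout and at most about a third of a standard error over the assumed 12-25% range of placebo dropout, in either direction. The flag ranges from a label swap to a large distortion of the weighted effect, depending on undefined macro variables and on the effect in dropouts. This should be fixed because these two analyses are the SAP's stated evidence on the missing-data assumption.

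**What to change.** State one value list for TRT01PN and TRTPN in the SAP and align the code to it:
- **If placebo is 1:** define DOSE1 and DOSE2 from codes 2 and 3 in 3a, and revise the TRTPN ESTIMATE and CONTRAST coefficients. Leave the exclusion and control level in 3b.
- **If placebo is 3:** change the 3b exclusion to IN (1,2) and the control level to 3.
- **In either case:** set DROP to 0 for completers and 1 otherwise, define `&grp11` to `&grp23`, and name placebo with REF= in the logistic CLASS statement.

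If programs already exist, confirm their donor and reference arms before unblinding. The cost is one value list and a few lines of sample code.

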6.6. STATISTICAL TESTS

The default significance level will be (5%); confidence intervals will be 95% and all tests will be two-sided, unless otherwise specified in the description of the analyses.

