15.2.3.3. Analysis of Proportion of patients achieving a treatment response

Patients having a 50% or greater improvement from baseline in MADRS total score will be defined as "responders". Patients having a negative percentage change indicate improvement in MADRS total score. The proportion will be evaluated using logistic regression. The responder indicator will be set to 1 if the percentage improvement is greater than or equal to 50%, set to 0 if less than 50%, or set to missing if the percentage is missing. The responder variable will be modeled using treatment and pooled study center as a categorical factor, and baseline MADRS total score as a covariate. If the model fails to converge, the model will be attempted with country (in place of pooled center) and baseline MADRS total score. If the model still does not converge then geographic region will be used (in place of country). Contrasts will be evaluated for each SM-13496 treatment group compared to placebo. Odds Ratios, 95% CIs and Wald chi-square p-values will be presented for each contrast. Only n and percent will be presented in cases where the number of patients meeting the above composite variable criteria is too small for an analysis to be performed.

A Cochran-Armitage trend test will also be conducted on this outcome across placebo and the two SM-13496 treatment groups. In addition, the number needed to treat (NNT) to attain an additional responder will be derived for each SM-13496 dose group as follows:

$$\text{NNT} = 1 / \text{Risk Reduction}$$

where Risk Reduction (RR) = (SM-13496 response rate – placebo response rate). NNT results will be provided in whole numbers with any fractional values rounded up to the nearest whole number. The 95% CIs will also be presented and are computed by taking the reciprocal of the 95% lower and upper bounds of the RR. The lower confidence limit will be rounded down to the largest integer value that is less than the computed estimate, and the upper confidence limit will be rounded up to the smallest integer value that is greater than the computed estimate.

Between-group effect size represented by Cohen's h will also be presented and will be derived as follows:

$$h = 2 \times \arcsin(\sqrt{\text{SM-13496 response rate}}) - 2 \times \arcsin(\sqrt{\text{placebo response rate}})$$

Document:	K:\DSP\SM-13496\KVA95374\Biostatistics\Documentation\SAP	Version Number:	1.0
Author:	[REDACTED]	Version Date:	30MAR2017

Template No: CS_TP_BS016 – Revision 3

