Effective Date: 01May2012

Reference: CS_WI_BS005

Copyright © 2012 [REDACTED] All rights reserved.
The contents of this document are confidential and proprietary to [REDACTED]. Unauthorized use, disclosure or reproduction is strictly prohibited.

This analysis will be performed for the ITT population, and will be repeated by country. Similar responder classifications are defined for subjects with 20%, 30%, and 40% or greater improvement from baseline in MADRS total score. Subjects classified as 20%, 30% and 40% responders will be analyzed as in the previous paragraph, with the exception of the Cochran-Armitage test which is exclusive to the 50% analysis.

This analysis will be repeated for a subgroup of patients who also achieved response criteria on the CGI-BP-S scale. This is classed as a CGI-BP-S score ≤ 3 .

The time to response of MADRS will be analyzed using a time-to-event analysis. Patients failing to achieve a response during the study period will be censored at the day of completion/discontinuation from the study. Kaplan-Meier results will be displayed for the 25%, 50% and 75% quartiles. Additionally, the Kaplan-Meier estimates of the response rate for each treatment group will be displayed. A log-rank test will also be used to compare SM-13496 with placebo, and also compare the two SM-13496 doses. A Kaplan-Meier figure will also be produced to support the analysis.

The time-to-event analysis will also use a Cox proportional hazards model with fixed effects for treatment, geographic region and baseline MADRS total score as a continuous covariate. This model will be used to generate hazard ratios for the same comparisons as specified for the log-rank test.

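### The NNT confidence interval in SAP 15.2.3.3 and Appendix 3 item 6 is invalid whenever the interval for the response difference contains 0, and its coded rounding contradicts the text

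*SAP*

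**What the plan says.** SAP 15.2.3.3 defines the NNT as one over the difference in response rates, drug minus placebo. It says that the 95% limits "are computed by taking the reciprocal of the 95% lower and upper bounds of the RR", where RR is that difference. The lower NNT limit is to be rounded down, the upper limit up, and the NNT itself up to a whole number. The section does not mention truncation or a difference interval that spans 0. SAP 6.6 sets the general convention: "confidence intervals will be 95% and all tests will be two-sided".

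Appendix 3 item 6 does something else. It computes unadjusted Wald limits, starting "delta_la = pi0a - pi1 - 1.96*sqrt(pi1*(1-pi1)/PCOUNT", and then branches on the sign of the estimate:

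- Under "if pi0a>=pi1 then do", it floors the lower difference limit: "upper_ba = max(delta_la, 0.000001".
- In the other branch, it caps the upper difference limit: "lower_ba = min(delta_ua, -0.000001".

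The reciprocals are then rounded before the outward function is applied, as in "lcia = floor(round(1/lower_ba", with `ceil` of `round` for the upper limit.

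On scope, SAP 15.2.3.3 states: "This analysis will be performed for the ITT population, and will be repeated by country". The same methods apply to the 20%, 30% and 40% response thresholds and, through SAP 15.2.3.4, to remission.

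**The concern.** The reciprocal of an interval that contains 0 is not an interval. It is two pieces, one running from a finite NNT for benefit up to infinity and the other from infinity back to a finite NNT for harm. The text inverts the two ends as if the result were one ordinary interval. The code discards one of the pieces and puts a programming constant in its place.

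A table built on these limits would show an NNT interval lying wholly on the side of the point estimate, although the data are compatible with an effect in the other direction. The rounding conflict is a separate matter and affects significant results as well, because it can make a limit narrower than the stated rule allows.

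**Working it through.** **Inputs.** The Wald formula, branches and rounding are from Appendix 3 item 6, and the rounding rule and reciprocal definition are from SAP 15.2.3.3. Group sizes of 161 and 167 are from protocol section 3.5. The documents give no response rates and no NNT figure, so there is no stated NNT result to reproduce, and every response rate below is an assumption. As a check on the group size, effect size 0.35 with 161 per arm and both p-values at or below 0.05 gives complete power of 80.4%, against the protocol's 80%.

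**Formulas.** d = p1 - p0; SE = sqrt[p0(1 - p0)/n0 + p1(1 - p1)/n1]; limits d ± 1.96 SE; NNT limits 1/(upper limit of d) and 1/(lower limit of d).

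**1. Difference interval contains 0, drug above placebo.** Assume 42% against 34%, 167 per arm.

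- d = 0.080, SE = 0.0529, limits -0.024 to 0.184, NNT = 1/0.080 = 12.5.
- Text: the reciprocals are -42 and 5.4. The range from -42 to 5.4 does not include 12.5.
- Code: the lower difference limit is replaced by 0.000001, and 1/0.000001 = 1,000,000. The result is 5 to 1,000,000.

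The constant does not depend on the data. With 64/161 against 48/161 the difference interval is -0.004 to 0.203 and the code gives 5 to 1,000,000. The harm side, which starts at 1/0.0041 = 244, has gone.

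**2. Difference interval contains 0, drug below placebo.** Assume 45/161 against 48/161.

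- d = -0.019, limits -0.118 to 0.080.
- Code: the upper difference limit is replaced by -0.000001, so the result is -1,000,000 to -9. The benefit side, which starts at 1/0.0804 = 12.4, has gone.

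On a grid of 32-64 placebo and 32-112 drug responders at 161 per arm, all 946 cells whose interval contained 0 were truncated: 563 to an upper limit of 1,000,000 and 383 to a lower limit of -1,000,000.

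**3. Rounding.** Once `round` has been applied, `floor` and `ceil` do nothing. For any x, floor(x) ≤ round(x) ≤ ceil(x), so the coded limit equals the text's limit or lies inside it, and never outside. With 72/161 against 48/161 (difference interval 0.0447 to 0.2534), the unrounded limits are 3.95 and 22.37. The code gives 4 to 22 and the text rule 3 to 23. Across the 1,582 grid cells with significant benefit, each limit differed from the text rule in 48% and at least one limit in 71%.

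**4. How often the difference interval contains 0.** Effect sizes are converted to response rates by a latent-normal shift, an assumption, with 30-40% placebo response. The by-country row is by exact binomial enumeration.

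| Assumed setting | Interval contains 0 |
|---|---|
| Effect size 0.45 (prior study's result, protocol 3.5), 161-167 per arm | about 9-11% |
| Effect size 0.35 (planning value, protocol 3.5), 161-167 per arm | about 27-31% |
| 10-point and 8-point difference, 30% placebo, 167 per arm | about 51% and 66% |
| By country, 40% against 30%, 6-60 per arm | about 78-87% |

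The country sizes are in line with SAP Table B. Japan's nine pooled centers total 179 patients, about 60 per arm, and Malaysia has 19, about 6 per arm. Within the by-country 78-87%, about 11-22 percentage points fall in the branch that hides possible benefit.

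**5. Two further mismatches in the same code.** Equal observed rates make the NNT line divide by zero; this happens in about 22% of such comparisons at 6 per arm and 4% at 60. The code also keeps the NNT to 0.01, where the text wants a whole number rounded up.

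**The case against.** A reader might infer that the method systematically favors the drug by hiding harm. The documents do not support that. The truncation follows the sign of the observed difference, and in the other branch it is possible benefit that disappears.

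A reader might also infer that the secondary results in general carry wrong error bars. They do not. SAP 15.2.3.3 also gives an odds ratio, its 95% interval and a Wald p-value from the adjusted logistic model for each contrast, and there a lack of significance would normally be visible. The NNT is not among the protocol's variables (sections 3.4.1 and 9.5.3) and stands outside the Hochberg procedure. The trigger for the defect is the unadjusted Wald interval in the code, which can disagree with the adjusted logistic p-value near the boundary.

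Three further points have some force. Appendix 3 only computes the limits; the output templates are not in the documents, so 1,000,000 might be displayed as infinity, though the SAP does not say so. SAP 15.2.3.3 falls back to counts and percentages when numbers are too small to analyze, which may suppress some small-country cases. And the rounding error is less than one whole unit; in the 42% against 34% example (5.44 to 5) code and text agree on the lower limit.

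These points limit the consequences. None makes the computed limits valid, and even a display of infinity would still omit the opposite side.

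**Conclusion.** The point holds, within limits. Whenever the unadjusted Wald 95% interval for the response difference contains 0, neither the text nor the code yields a valid NNT interval, and the side that is lost depends on the sign of the estimate. The coded rounding contradicts the text; in the grid examined it made each limit too narrow in about half of the cases, and it cannot make one too wide.

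The defect itself follows from the formulas and needs no assumed rates. Its frequency does: about 27-31% of overall comparisons at the planning effect size, fewer at the effect seen in the prior study, and most by-country comparisons. The higher figures of 51-66% apply only if the true difference is 10 to 8 points with 30% placebo response, and should not be read as what the protocol's planning assumption implies. The effect is confined to a supplementary descriptive measure. The change should be made, but no conclusion on the primary endpoint depends on it.

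**What to change.** 1. Delete both truncations, 0.000001 and -0.000001, from Appendix 3 item 6.
2. Report the risk difference with its 95% interval wherever an NNT is given.
3. When that interval contains 0, show the NNT interval as NNT for benefit through infinity to NNT for harm, or state that no finite interval exists. Add a sentence saying so to SAP 15.2.3.3.
4. Apply `floor` and `ceil` directly to the unrounded reciprocals.
5. Add a rule for equal rates, and make the NNT in the code a whole number rounded up, as the text requires.

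The cost is a few lines of code and a sentence or two of text. No new data are needed and no other analysis changes.
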